APPENDIX 2. FAGERSTRÖM TEST OF NICOTINE DEPENDENCE

The Fagerström Test of Nicotine Dependence (FTND) has been shown to be a reliable and valid measure of nicotine dependence²² and will be administered at the randomization visit only. Analysis of results is outlined in the study Statistical Analysis Plan.

Question	Response
How soon after you wake up do you smoke your first cigarette?	Within 5 minutes
	6-30 minutes
	31-60 minutes
	After 60 minutes
Do you find it difficult to refrain from smoking in places where it is forbidden (for example in church, at the library, in a cinema, etc.)?	Yes
	No
Which cigarette would you hate most to give up?	The first one in the morning
	All others
How many cigarettes/day do you smoke?	10 or less
	11-20
	21-30
	31 or more
Do you smoke more frequently during the first hours after waking than during the rest of the day?	Yes
	No
Do you smoke if you are so ill that you are in bed most of the day?	Yes
	No

APPENDIX 3. SMOKING SELF-EFFICACY QUESTIONNAIRE (SEQ-12)

The Smoking Self-Efficacy Questionnaire (SEQ-12)²³ is a validated instrument to assess baseline situations in which people might be tempted to smoke and will be administered at the randomization visit only. Analysis of results is outlined in the study Statistical Analysis Plan.

The following are some situations in which certain people might be tempted to smoke. Please indicate whether you are sure that you could refrain from smoking in each situation using one of the following answers:

	1 = Not at all sure	2 = Not Very Sure	3 = More or less sure	4 = Fairly Sure	5 = Absolutely Sure
1. When I feel nervous	1	2	3	4	5
2. When I feel depressed	1	2	3	4	5
3. When I am angry	1	2	3	4	5
4. When I feel very anxious	1	2	3	4	5
5. When I want to think about a difficult problem	1	2	3	4	5
6. When I feel the urge to smoke	1	2	3	4	5
7. When having a drink with friends	1	2	3	4	5
8. When celebrating something	1	2	3	4	5
9. When drinking beer, wine, or other spirits	1	2	3	4	5
10. When I am with other smokers	1	2	3	4	5
11. After a meal	1	2	3	4	5
12. When having coffee or tea	1	2	3	4	5

APPENDIX 4. BRIEF QUESTIONNAIRE OF SMOKING URGES (QSU-BRIEF)

The 10-question Brief Questionnaire of Smoking Urges (QSU-Brief) has been validated as a self-report instrument to measure tobacco craving/urges^{24,25} and will be administered to study subjects at randomization and clinic visits on Day 7, 14, 21, 28, 35, and 42. Analysis of results is outlined in the study Statistical Analysis Plan.

We are interested in how you are thinking or feeling right now as you are filling out the questionnaire:

Question	Response						
	Strongly Disagree.....Strongly Agree						
	1	2	3	4	5	6	7
I have a desire for a cigarette right now.							
Nothing would be better than smoking a cigarette right now.							
If it were possible, I probably would smoke now.							
I could control things better right now if I could smoke.							
All I want right now is a cigarette.							
I have an urge for a cigarette.							
A cigarette would taste good now.							
I would do almost anything for a cigarette now.							
Smoking would make me less depressed.							
I am going to smoke as soon as possible.							

APPENDIX 5. MINNESOTA WITHDRAWAL SCALE (MNWS)

Several versions of the Minnesota Withdrawal Scale (MNWS) have been used since 1986. The version used in this study has been shown to provide specific assessment of nicotine withdrawal using 9 specific items.^{26,27} The questionnaire will be administered to all study subjects at randomization and then weekly starting on Week 1 through Week 7 clinic visits. Analysis of results is outlined in the study Statistical Analysis Plan.

For each of the following, please rate yourself on how you have been feeling over the past 24 hours. Mark the number that applies to you:

Question	Response				
	Not at all	Slight	Moderate	Quite a bit	Extreme
Urge to smoke ^{item 1}	0	1	2	3	4
Depressed mood ^{item 2}	0	1	2	3	4
Irritability, frustration, or anger ^{item 3}	0	1	2	3	4
Anxiety ^{item 4}	0	1	2	3	4
Difficulty concentrating ^{item 5}	0	1	2	3	4
Restlessness ^{item 6}	0	1	2	3	4
Increased appetite ^{item 7}	0	1	2	3	4
Difficulty going to sleep ^{item 8}	0	1	2	3	4
Difficulty staying asleep ^{item 9}	0	1	2	3	4

APPENDIX 6. HOSPITAL ANXIETY AND DEPRESSION SCALE (HADS)

The HADS questionnaire²⁸ has been validated as a self-report instrument to measure levels of anxiety and depression and will be administered to study subjects. This questionnaire must be completed by all potential study subjects (completed = each of the 14 questions must be answered by the subject) during screening. The HADS questionnaire must be reviewed by clinic staff and a summation score calculated by totalling the numbers circled for each question at Screening Visit #1. A score ≥ 11 (**total of Depression “D” Questions only**) indicates current symptoms of moderate to severe depression and will be considered exclusionary for this study. The HADS questionnaire is to also be completed at Day 42 (Week 6) and again at Day 86 (Week 12). Analysis of results is outlined in the study Statistical Analysis Plan.

A	I feel tense or 'wound up':
3	Most of the time
2	A lot of the time
1	From time to time, occasionally
0	Not at all
D	I still enjoy the things I used to enjoy:
0	Definitely as much
1	Not quite so much
2	Only a little
3	Hardly at all
A	I get a sort of frightened feeling as if something awful is about to happen:
3	Very definitely and quite badly
2	Yes, but not too badly
1	A little, but it doesn't worry me
0	Not at all
D	I can laugh and see the funny side of things:
0	As much as I always could
1	Not quite so much now
2	Definitely not so much now
3	Not at all
A	Worrying thoughts go through my mind:
3	A great deal of the time
2	A lot of the time
1	From time to time, but not too often
0	Only occasionally
D	I feel cheerful:
3	Not at all
2	Not often
1	Sometimes
0	Most of the time

D	I feel as if I am slowed down:
3	Nearly all the time
2	Very often
1	Sometimes
0	Not at all
A	I get a sort of frightened feeling like 'butterflies' in the stomach:
0	Not at all
1	Occasionally
2	Quite Often
3	Very Often
D	I have lost interest in my appearance:
3	Definitely
2	I don't take as much care as I should
1	I may not take quite as much care
0	I take just as much care as ever
A	I feel restless as I have to be on the move:
3	Very much indeed
2	Quite a lot
1	Not very much
0	Not at all
D	I look forward with enjoyment to things:
0	As much as I ever did
1	Rather less than I used to
2	Definitely less than I used to
3	Hardly at all
A	I get sudden feelings of panic:
3	Very often indeed
2	Quite often
1	Not very often
0	Not at all

A	I can sit at ease and feel relaxed:
0	Definitely
1	Usually
2	Not Often
3	Not at all

D	I can enjoy a good book or radio or TV program:
0	Often
1	Sometimes
2	Not often
3	Very seldom

Note: The actual questionnaire will not indicate the category (A=anxiety, D=depression) or the points, which are provided here to show how responses will be scored for analysis.

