APPENDIX 1. COLUMBIA - SUICIDE SEVERITY RATING SCALE (C-SSRS)

The Columbia Suicide Severity Rating Scale (C-SSRS) provides a standardized method to assess both suicidal ideation and behaviour to identify those at risk for suicide.²¹ The questionnaire must be administered by trained study staff* at Screening and again at the Week 6 (Day 42) and Week 12 (Day 86) study visits. Assessments at Screening will utilize the “Screening” version of the form with ideation to be assessed in the past 3 months and suicidal behaviour within lifetime (the later assessment timing helps to discern if later positive assessments are possibly treatment emergent). Any “Yes” to question 4 or 5 OR “Yes” to any suicidal behaviour question with clear suicidal intent or previous attempt will be considered exclusionary for this study. Assessments at Week 6 (Day 42) and Week 12 (Day 86) study visits will utilize the “Since Last Visit” version of the form with timeframe to be “since last assessment”. Any “Yes” to question 4 or 5 OR “Yes” to any suicidal behaviour question at the Week 6 (Day 42) or Week 12 (Day 86) study visits requires reporting as an AE as well as referral to a qualified Mental Health Professional for follow-up.

*Training by study staff is to be documented via certification in past 1 year on the C-SSRS. Training can be obtained on-line (www.cssrs.columbia.edu/training/training-research-setting).

COLUMBIA-SUICIDE SEVERITY RATING SCALE (C-SSRS)

Screening

Version 1/14/09

Posner, K.; Brent, D.; Lucas, C.; Gould, M.; Stanley, B.; Brown, G.; Fisher, P.; Zelazny, J.; Burke, A.; Oquendo, M.; Mann, J.

Disclaimer:

This scale is intended to be used by individuals who have received training in its administration. The questions contained in the Columbia-Suicide Severity Rating Scale are suggested probes. Ultimately, the determination of the presence of suicidal ideation or behavior depends on the judgment of the individual administering the scale.

Definitions of behavioral suicidal events in this scale are based on those used in The Columbia Suicide History Form, developed by [name] and [name], Conte Center for the Neuroscience of Mental Disorders (CCNMD), New York State Psychiatric Institute, [name]. (Oquendo M. A., Halberstam B. & Mann J. J., Risk factors for suicidal behavior: utility and limitations of research instruments. In M.B. First [Ed.] Standardized Evaluation in Clinical Practice, pp. 103 -130, 2003.)

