4.2.1.3. Other Adverse Events of Special Interest

The following events will be reported as “other adverse events of special interest”:

- Treatment-emergent suicidal ideation or risk, as measured by responses on the C-SSRS on or after first dose of study drug. Suicidal ideation or risk will be defined as a response of “Yes” to either question 4 or question 5 or “Yes” to any suicidal behavior question on the C-SSRS.

Note: Suicidal ideation or risk for suicide prior to randomization (“Yes” to either question 4 or question 5 OR “Yes” to any suicidal behavior question on the C-SSRS) is an exclusion criterion.

- Treatment-emergent moderate to severe depression, as measured by a HADS depression score ≥ 11 on or after first dose of study drug.

Note: Current symptoms of moderate to severe depression prior to randomization (HADS depression score ≥ 11) is an exclusion criterion.

- New pregnancy documented by a positive pregnancy test on or after first dose of study drug.

Note: Pregnancy is an exclusion criterion.

- Treatment-emergent coronavirus disease 2019 (COVID-19) will be selected using the Medical Dictionary for Regulatory Activities (MedDRA) standardized MedDRA query (SMQ) for COVID-19.

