6.2. General Considerations

Statistical analyses will be performed at the end of the study after the last subject has completed the Week 24 visit, all data have been reported, cleaned, and the eCRF database has been locked.

Medical history events and adverse events will be coded to standard “preferred terms” and “system organ classifications (SOC)” using the Medical Dictionary for Regulatory Activities (MedDRA) Version 23.1 or higher. Concomitant medications will be coded using the World Health Organization Drug Dictionary (WHODrug) Version Mar-2021 B2 or higher.

All statistical programming will be done using SAS® Version 9.4 or higher (SAS® Institute, Cary, North Carolina). All tables, figures and listings will be produced in landscape format.

In general, all data will be listed by treatment arm, subject and visit/time point where appropriate. The summary tables will have columns corresponding to, or be stratified by, treatment arm. In listings and summary tables the treatment arms will be ordered and labelled as follows: Placebo, Cytisinicline 6 Weeks, Cytisinicline 12 Weeks.

The total number of subjects under the stated analysis set in each treatment arm (N) will be displayed in the header of summary tables.

Data will be summarized using descriptive statistics for continuous variables. Unless otherwise specified, descriptive statistics will include number of subjects (n), mean, standard deviation, minimum, median and maximum. In case of $n < 2$, where n indicates the number of subjects with evaluable data at the particular time point, the standard deviation will be empty. The statistic “Missing” will also be presented as the number of missing entries/subjects, if any at that visit/timepoint, and presented as a summary statistic only when non-zero. The minimum and maximum statistics will be presented to the same number of decimal places as the original data. The mean and median will be presented to one more decimal place than the original data, whereas the standard deviation will be presented to two more decimal places than the original data.

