6.4.2. Questionnaire Scoring

This section describes scoring for the questionnaires that will be used in the study. No imputation will be done for missing item responses on the questionnaires. Total scores will only be computed if there are no missing item scores.

Fagerstrom Test of Nicotine Dependence (FTND)

The FTND is a 6-item multiple-choice questionnaire (see Appendix 2 of the study protocol). It will be administered at SV1. An FTND total score will be derived for each subject providing all questions have been answered, using the scoring key that follows:

Item #	Item Text	Item Response	Item Score
1	How soon after you wake up do you smoke your first cigarette?	Within 5 minutes	3
		6–30 minutes	2
		31–60 minutes	1
		After 60 minutes	0
2	Do you find it difficult to refrain from smoking in places where it is forbidden (eg, in church, at the library, in the cinema, etc.)?	Yes	1
		No	0
3	Which cigarette would you hate most to give up?	The first one in the morning	1
		All others	0
4	How many cigarettes/day do you smoke?	10 or less	0
		11 – 20	1
		21 – 30	2
		31 or more	3
5	Do you smoke more frequently during the first hours after waking than during the rest of the day?	Yes	1
		No	0
6	Do you smoke if you are so ill that you are in bed most of the day?	Yes	1
		No	0

Smoking Self-efficacy Questionnaire (SEQ-12)

The SEQ-12 is a 12-item questionnaire that will be administered at the Day 0 visit. Item scores will be assigned using the scoring key pre-printed on the questionnaire (see Appendix 3 of the study protocol). Three scores will be derived for each subject providing there are no missing questions: SEQ-12 internal stimuli score (items 1-6), external stimuli score (items 7-12) and a total score (items 1-12).

Hospital Anxiety and Depression (HADS)

The HADS questionnaire will be administered at SV1, Week 6 and Week 12. Item scores will be assigned using the scoring key pre-printed on the questionnaire (see Appendix 6 of the study protocol). Providing there are no missing questions, total scores for depression and anxiety and overall will be derived for each subject.

Brief Questionnaire of Smoking Urges (QSU-Brief)

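### Staff must total the HADS only at screening, so an on-study depression score of 11 or more needs no same-visit review, and one blank item removes that visit's score even when the answered items already reach 11

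*Protocol*

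**What the plan says.** Protocol Appendix 6 uses the HADS at screening to exclude subjects whose depression items total 11 or more. For that purpose clinic staff review the form, with "a summation score calculated by totalling the numbers circled for each question at Screening Visit #1". For the on-study visits it adds only this: "The HADS questionnaire is to also be completed at Day 42 (Week 6) and again at Day 86 (Week 12". The visit lists in Section 12.2.3 ask the subject to complete the form at Week 6 and Week 12. Section 8.3.2 and footnote 3 of Table 4 carry the Week 12 assessments over to early discontinuation. The closing note to Appendix 6 says: "The actual questionnaire will not indicate the category (A=anxiety, D=depression) or the points".

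The SAP gives the score a safety role. Section 2.1 lists the HADS among the safety assessments done at clinic visits. Section 4.2.1.3 names as an event of special interest "Treatment-emergent moderate to severe depression, as measured by a HADS depression score" of 11 or more on or after first dose, and Section 11.1.2 reports it as number and percentage by arm.

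On scoring, SAP 6.4.2 states the general rule, "Total scores will only be computed if there are no missing item scores", and for the HADS: "Providing there are no missing questions, total scores for depression and anxiety and overall will be derived for each subject". On timing, SAP 6.2 says: "Statistical analyses will be performed at the end of the study after the last subject has completed the Week 24 visit".

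**The concern.** There are two separate gaps.

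The first is at the site. A subject can reach the entry-exclusion level of depressive symptoms at Week 6 and carry on dosing without anyone being required to know the total. The protocol does promise follow-up of abnormalities that the investigator judges clinically significant (Synopsis, Study Procedures; Section 14), but a total that has not been added up cannot prompt that judgement. Week 6 matters most, because it is the only scheduled on-study HADS after which dosing continues. At Week 12 and at early discontinuation, what may be lost is timely clinical follow-up.

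The second is in the derivation. Items score from 0 upward, so the sum of the answered items is a lower bound on the true total. A rule that discards a form whose lower bound is already 11 or more throws away a known event. Any effect on the event count is downward.

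**Working it through.** The plan states no figure to reproduce. The check is a comparison of the text followed by arithmetic on the scale.

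**Who looks at what, and when**

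| Safety measure | On-study action stated |
|---|---|
| C-SSRS, Weeks 6 and 12 | Staff administer and assess it; a positive answer "requires reporting as an AE as well as referral to a qualified Mental Health Professional for follow-up" (Appendix 1) |
| Laboratory results | Investigator judges significance; significant results go on the AE form (Section 14.3.1) |
| HADS, Weeks 6 and 12, early discontinuation | Subject completes the form; no totalling, threshold check or action |

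The only on-study scoring that the documents state is the SAP derivation, for analyses run after the last Week 24 visit.

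**Schedule around the on-study forms** (Section 12.2.3; Tables 4 and 5)

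- Week 6 is Day 42 and the last dose is Day 84: 84 − 42 = 42 dosing days, 42 × 3 = 126 tablets, and in Arm C 126 × 3 mg = 378 mg cytisinicline. Arms A and B take placebo in this period.
- Next scheduled HADS: 86 − 42 = 44 days later. Weekly visits with AE questions continue in between, the next on Day 49.
- Week 12 HADS is Day 86, after the last dose. The next visit, Week 16, is nominally Day 16 × 7 = 112, so 112 − 86 = 26 days later. No further HADS is scheduled.

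**Blank items**

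Inputs from Appendix 6: 7 depression items, each 0 to 3, maximum 7 × 3 = 21, threshold 11. Let S be the sum of the answered depression items and b the number left blank. The true total lies between S and S + 3b. The event is therefore certain if S ≥ 11, excluded if S + 3b ≤ 10, and otherwise undetermined.

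| b | Largest possible S | Event certain | Event excluded | Undetermined |
|---|---|---|---|---|
| 1 | 6 × 3 = 18 | 11–18 | 0–7 | 8–10 |
| 2 | 5 × 3 = 15 | 11–15 | 0–4 | 5–10 |
| 3 | 4 × 3 = 12 | 11–12 | 0–1 | 2–10 |
| 4 | 3 × 3 = 9 | none | none | 0–9 |

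Up to three depression items can thus be blank with the event already established. SAP 6.4.2 gives no score in any of these rows. Read literally, its HADS sentence also withholds the depression score when only an anxiety item is blank, although all seven depression items, and hence a total of up to 21, are known.

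**How often**

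The documents give no blank-item rate. Suppose, as an assumption, that each item is blank independently with probability q between 0.1% and 2%. The share of forms with at least one blank is 1 − (1 − q)^7 = 0.7% to 13.2% over the depression items, and 1 − (1 − q)^14 = 1.4% to 24.6% over the whole form. These are shares of incomplete forms, not of hidden events. The latter would also need the frequency of high scores, which is not given.

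**The case against.** Several points on the other side have force.

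- *Completeness on study.* Appendix 6 explains completion, in brackets, as all 14 questions answered, and a few lines later uses the same verb for Weeks 6 and 12. The definition plausibly carries over. A reader might infer that the plan tolerates blank items on study; the text does not support that. The scoring gap then concerns only residual incomplete forms.
- *The subject is not lost.* It is tempting to say that the SAP rule drops the subject from the safety analysis. It does not. Only that visit's score is missing. The subject stays in the Safety Set and can still count through another visit's form or appear in the AE tables.
- *Exposure.* The 378 mg and 44 days might be read as harm that the change would prevent. They describe the planned schedule. A score of 11 is an entry threshold, not a stopping rule, and review need not end dosing.
- *Other nets.* Weekly AE questions, the C-SSRS at the same visits and the depressed-mood item of the MNWS through Week 7 may catch some of these subjects. Protocol Section 14 also lets safety procedures be done at any time. None of these requires the HADS total to be looked at.
- *Sites can score the form.* They do so at screening, and the answer wording remains visible even though points and categories are hidden. This lowers the cost of a change but supplies no instruction.
- *The C-SSRS contrast.* Suicidal intent or behaviour justifies a stricter rule than a symptom score, and the protocol itself reserves the special-interest label for COVID-19 matters (Section 14.2.5). The difference is not a contradiction. It does show that same-visit handling of a questionnaire was feasible.
- *Unseen documents.* The study manuals, eCRF, Data Entry Guidelines and DSMC charter may hold a scoring step. The first gap rests on the absence of one in the two documents available.

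**Conclusion.** Both gaps hold, and they should be closed. Followed as written, the protocol and SAP can leave an on-study depression score of 11 or more without review until the final analysis, and can omit from a visit's event count a form whose answers already prove the event.

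The effect on the count runs one way: it can be too low, never too high. The percentage is less clear-cut, because SAP 6.2 divides by subjects with non-missing values and the present rule also removes incomplete forms that are certainly negative.

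The size in subjects cannot be stated without rates that the documents do not give. The conclusion assumes that no unseen manual already requires on-study scoring, and for the second gap that some on-study forms arrive incomplete despite Appendix 6. The documents do not show that any subject is harmed, or that depression would generally go unnoticed. The primary and secondary efficacy analyses, power and type I error are unaffected.

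**What to change.** **Protocol Appendix 6 and Section 12.2.3.** At Week 6, Week 12 and early discontinuation, staff check that all 14 items are answered and total the 7 depression items with the key used at screening. The investigator reviews any total of 11 or more at that visit and records an AE if it is judged clinically significant, as is already done for laboratory results. State that this is a review, not a stopping rule. If a study manual already holds such a step, a cross-reference is enough.

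**SAP 6.4.2 and 4.2.1.3.** Derive the depression total from the 7 depression items alone, so that a blank anxiety item has no effect on it. Where depression items are blank, count an event if the answered sum is 11 or more, count a non-event if that sum plus 3 per blank item is 10 or less, and list the remainder as undetermined. Keep both determined groups in the denominator; restoring only the certain positives would push the percentage up.

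**Cost.** A few minutes per form at visits already planned, short additions to the protocol and the SAP, and some added AE records where the investigator judges the score significant. No new visit or form is needed.
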